4. Child is not in behavioral weight-loss treatment (behavior weight-loss treatment will not include if their pediatrician is counseling them on their weight, but instead refers to intensive outpatient behavioral treatment for overweight/obesity only)
5. Child and parent do not have a history of seizures, a history of severe psychiatric conditions such as Schizophrenia or Paranoia, or use any medical devices such as pacemakers
6. Child is not exhibiting any disordered eating behavior (i.e. purging, laxative or diuretic use).

E2.B. Exclusion Criteria

1. Parent is not biological or legal guardian and therefore cannot consent on behalf of the child
2. Parent BMI is less than 25 (not overweight or obese)
2. Parent is over 80 years old and/or child is younger than 6 or older than 12
3. Child BMI is below the 85th percentile for age and sex.⁵¹
4. Child is in behavioral weight-loss treatment (behavior weight-loss treatment will not include if their pediatrician is counseling them on their weight, but instead refers to intensive outpatient behavioral treatment for overweight/obesity only)
5. Child and parent have a history of seizures, a history of severe psychiatric conditions such as Schizophrenia or Paranoia, or use any medical device such as a pacemaker
6. Child has a history of disordered eating behavior (i.e. purging, laxative or diuretic use).

E2.C. Ethical Considerations

All key personnel involved in the design or conduct of research involving human subjects will receive the required education on the protection of human research participants prior to the start of the study. Participants will be informed that they do not have to answer any questions that make them uncomfortable. There are minimal risks for participating in pilot testing. Testing and assessments will occur in private rooms to protect the anonymity of the participant.

Participants will be provided with the contact information of the research staff. As a clinical psychologist, the PI is trained in how to address safety issues. The PI, a licensed psychologist, will be available for in-person crisis assessment. Any participants that indicate they are engaging in disordered eating behaviors during screening or participation in the study will be offered referral information for in-person treatment. Any adverse event will be reported promptly to the IRB.

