Confidentiality: Participant confidentiality will be maintained in compliance with HIPAA privacy protected servers. Study IDs will be linked with participant names and email addresses in a separate password-protected file stored on a secure, password-protected server that only key study personnel have access to. All hard copy PHI will be stored in locked cabinets within locked doors in our laboratory at WUSM. All employees of the study with access to PHI are required to complete HIPAA training and comply with the privacy procedures in place at Washington University.

BehaVR (<https://behavr.com>) is a HIPAA-compliant company focused on building VR products for behavior change and has a dedicated and talented team of software engineers. BehaVR will host the proposed VR experience and all data collected within the VR experience. Prior to beginning this study, BehaVR and Washington University will enter into a collaboration agreement.

Adverse Events: For the purpose of this study, adverse events will be defined as unanticipated problems involving risks to the study participant. A serious adverse event will be defined as any untoward occurrence that results in death, is life-threatening, or creates persistent and significant disability. The study team will work together to identify serious adverse events. Any potentially adverse events will be evaluated by the study team within 72

hours. All serious adverse events will be immediately reported to the IRB. All adverse events and study withdrawals, together with a detailed explanation of the event and withdrawal, will be recorded.

It is important to note that in previous studies of digital health interventions, the procedures outlined above have been used to protect against and minimize potential risks to participants, and they have proved effective in preventing emotional and physical complaints as well as adverse events.

E2.D. Participant Recruitment Plans and Consent Process

We plan to enroll 60 English-speaking children between the ages of 6 and 12 and one of their biological or legal adult guardians.

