condition will undergo the 10-minute VR experience (both children and parents) while those assigned to the control condition will view the educational video and play the educational game for a total of 10 minutes.

E2.F. Risks and Benefits

Risks: All key personnel involved in the design or conduct of research involving human subjects will receive the required education on the protection of human research participants prior to the start of the study. Participants will be informed that they do not have to answer any questions that make them uncomfortable. There are minimal risks for participating in pilot testing. Testing and assessments will occur in private rooms to protect the anonymity of the participant.

Participants will be provided with the contact information of the study staff. As a clinical psychologist, the PI is trained in how to address safety issues. If any participant appears to be in crisis during the experiment, appropriate action will be taken based on established crisis assessment protocol. All participants completing the experiment will be offered referral information for in-person treatment. Any serious adverse event will be reported promptly to the IRB.

Physical Risks: Participants will be engaging with the virtual environment through physical movement (e.g., stepping), and will be unable to see their surroundings (because they will be wearing a device over their eyes to engage with the VR experience), so the area in which individuals use the VR equipment will be open and clear of objects. Users will be monitored by trained staff to ensure they are safe when using the VR equipment. Finally, some individuals can feel motion sickness or nausea during a VR experience. Although this is not likely, participants will be told that if they do not feel well, they do not have to continue with the VR experience and that they can discontinue participation in this aspect of the study without penalty. Trained staff will assist in the event that participants need further care.

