1. Behavioral Beliefs and Intentions (Aim 2d)			
Attitudes, Beliefs, and Intentions	Theory of Planned Behavior Items	Parent and child self-report	Pre and post
1. Behavior (Aim 2d)			
Eating and Physical Activity Behavior	Weekly intake of fruits and vegetables; fast food; foods away from home; consumption of breakfast	Parent proxy-report	Pre and 2-week

	Screen time and minutes of mild, moderate, and vigorous activity over the past week		
1. Other Measures			
Body Mass Index (BMI)	In-lab height and weight	Parent & Child	pre
Demographics	Demographic Questionnaire	Parent report	pre
Hunger	1 item 7 point likert scale	Child report	pre
Affect	Positive and Negative Affect Schedule (PANAS)	Child	Pre and post
	Child Emotional Eating Scale Short Form (EES-C SF)	Child self-report	Pre and post
	Body Esteem Scale (adapted)	Child self-report	Pre and post

F3. Data Collection and Reporting Procedures for Adverse Events

For the purpose of this study, adverse events will be defined as unanticipated problems involving risks to the study participant. A serious adverse event will be defined as any untoward occurrence that results in death, is life-threatening, or creates persistent and significant disability. The study team will work together to identify serious adverse events. Any potentially adverse events will be evaluated by the study team within 72 hours. All serious adverse events will be immediately reported to the IRB. All adverse events and study withdrawals, together with a detailed explanation of the event and withdrawal, will be recorded.

It is important to note that in previous similar clinical trials of digital health interventions, the procedures outlined above have been used to protect against and minimize potential risks to participants, and they have proved effective in preventing emotional and physical complaints as well as adverse events.

G. Data Handling and Record Keeping

G1. Confidentiality and Security

Participant confidentiality will be maintained in compliance with HIPAA regulations. Data will be stored in locked file cabinets and on HIPAA privacy protected servers. Study IDs will be linked with participant names and email addresses in a separate password-protected file stored on a secure, password-protected server that only key study personnel have access to. All employees of the study with access to protected health information are required to complete HIPAA training and comply with the privacy procedures in place at Washington University.

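### The serious adverse event definition has no criterion for hospital admission or medical importance, so an admission that was not life-threatening and resolves is neither classed as serious nor covered by the immediate-report rule

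*Combined protocol and SAP*

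**What the plan says.** The definition stands twice in identical words, in the adverse events paragraph of E2.C and in F3: "A serious adverse event will be defined as any untoward occurrence that results in death, is life-threatening, or creates persistent and significant disability". Both places attach the fastest reporting rule to that class alone: "All serious adverse events will be immediately reported to the IRB".

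The wider class is defined more narrowly than its name suggests: "adverse events will be defined as unanticipated problems involving risks to the study participant". For it, E2.C and F3 set an evaluation limit ("Any potentially adverse events will be evaluated by the study team within 72 hours") and a recording rule ("All adverse events and study withdrawals, together with a detailed explanation of the event and withdrawal, will be recorded").

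The opening text of E2.C and the Performance Monitoring paragraph of G1 add a general promise: "Any adverse event will be reported promptly to the IRB". E2.F makes a promise of prompt IRB reporting for serious events only.

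On what could go wrong, E2.F says that participants move about in VR and "will be unable to see their surroundings", and it plans for a crisis: "If any participant appears to be in crisis during the experiment, appropriate action will be taken based on established crisis assessment protocol". E2.B excludes people with a past seizure or severe psychiatric illness.

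**The concern.** The three criteria catch the gravest outcomes and nothing below them. A short VR session, for children aged 6 to 12 and a parent, in a cleared and supervised space, is unlikely to cause death or lasting disability. If a grave event did occur, one plausible form is an admission for an injury, a seizure or a psychiatric crisis that was not life-threatening and then resolves. That form meets none of the three criteria.

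Two things are at stake. The first is how fast the IRB hears of such an event while other families are still being enrolled. The second is what the pilot can say about safety. Under these rules a statement of no serious adverse events could be literally true after a child had been admitted to hospital. D1 says that the pilot is meant to inform later grant applications, so that statement would be carried forward.

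**Working it through.** No arithmetic applies. The check sets every section that defines or routes an adverse event side by side and runs one test case through them.

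| Section | Events covered | What is promised |
|---|---|---|
| E2.C, opening text | any adverse event | prompt report to the IRB |
| E2.C, adverse events paragraph | serious: three criteria | immediate report to the IRB |
| E2.C, adverse events paragraph | potential adverse events | team evaluation within 72 hours |
| E2.C, adverse events paragraph | all adverse events and withdrawals | recorded with explanation |
| E2.F | serious events only | prompt report to the IRB |
| F3 | same as the E2.C adverse events paragraph | same |
| G1, Performance Monitoring | any adverse event | prompt report to the IRB |

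**Test case.** A participant is admitted after the session, was not in danger of dying, and recovers fully.

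1. *Is it serious?* Death: no. Threat to life: no. Lasting disability: no. It is not serious under E2.C or F3, and the immediate rule does not apply.
2. *Is it an adverse event?* Only if it is an unanticipated problem.
   - If it is, it is evaluated, recorded, and reported promptly under the opening text of E2.C and under G1. E2.F makes no promise for it.
   - If the team regards it as foreseen, it may fall outside the adverse event definition. An injury while stepping without sight could be read this way, since E2.F describes that risk and the precautions against it. The event would then be neither serious nor adverse, and could miss the general reporting and recording rules too.
3. *How fast would the IRB hear?* The documents put no time on either *immediately* or *promptly*. The only clock is the 72-hour evaluation limit. No section says whether reporting waits for it.

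Two inconsistencies come out of the table. Non-serious adverse events go to the IRB under the opening text of E2.C and under G1, but E2.F does not mention them. Serious events are reported immediately in the E2.C adverse events paragraph and in F3, but promptly in E2.F.

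The serious definition speaks of any untoward occurrence and does not itself carry the limit to unanticipated problems. Adding admission there would therefore catch the test case even where the harm was foreseen.

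**The case against.** The strongest reply is that the plan already covers most of this. An event that threatens life when it happens is serious even if it resolves, so a prolonged seizure or a suicidal crisis could already qualify. Any adverse event goes promptly to the IRB under E2.C and G1, and all are recorded with an explanation. The risk is low: staff monitor the session, the space is cleared, and people with relevant histories are excluded. Much of this stands, and it rules out several stronger readings.

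- *A reader might infer that such an admission would go unreported.* The documents do not support this. Where the event counts as unanticipated, two sections promise a prompt report. What remains is a gap in classification, the difference between two undefined words, and the conflict with E2.F.
- *A reader might infer a delay of up to 72 hours.* That figure limits evaluation, and it applies to any potential adverse event. No section makes the IRB report wait for it.
- *A reader might attach a probability to such an event.* The documents give no rate for injury, seizure or psychiatric admission, so any probability would only restate the rate assumed.
- *A reader might say that the protocol predicts fractures, first seizures or psychiatric admissions.* It does not. It names motion sickness, nausea and negative affect, describes movement without sight, plans for a crisis and excludes certain histories. The test case is a reasonable extension of that list.

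It can also be said that the SAP (section J) is in the past tense, so the trial may be over and a new reporting rule may change little. That limits the prospective gain. It does not affect how recorded events are classified when safety is reported.

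**Conclusion.** The point holds in a limited form. By the stated rule, an admission that was not life-threatening and resolves is not serious, and nothing requires it to be reported immediately. At most it is reported promptly as an adverse event. Even that route is uncertain, because E2.F speaks of serious events only and because the adverse event definition leaves out foreseen problems.

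The size is one class of event, missed in both places where the definition stands, with conflicting reporting rules across E2.C, E2.F, F3 and G1. It cannot be expressed as a probability or as a delay in hours. The conclusion rests on reading the three criteria as a complete list, which is how both sections present them. It also assumes that the team could treat an injury during movement without sight as foreseen; the text allows that reading but does not compel it. The change should be made because it is cheap and bears directly on whether a statement of no serious events can be trusted.

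**What to change.** 1. In E2.C and F3, add two criteria to the serious adverse event definition: hospital admission, and any event that the PI judges medically important.
2. In the same two places, remove the limit to unanticipated problems from the adverse event definition, so that foreseen harms are recorded.
3. State that a suspected serious event is reported to the IRB without waiting for the 72-hour evaluation.
4. Reconcile E2.C, E2.F, F3 and G1 on which events go to the IRB and when, and say what *immediately* and *promptly* mean in time.
5. If the trial is already complete, reclassify the recorded events under the extended definition before safety is reported. Read the recorded explanations for withdrawals as well, because a foreseen harm may not have been logged as an adverse event. Say in the report that such harms may be under-recorded.

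The cost is a wording amendment in the sections that carry the definitions and the reporting rules. Sample size, study visits and efficacy analysis do not change. Somewhat more events will be recorded, and an occasional event may be reported as serious and later downgraded.

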Univariate analyses of variance (ANOVA) models evaluated pre- to post-test changes in positive and negative affect by condition. T-tests evaluated the difference in acceptability measures between conditions. Repeated-measures general linear models, with time as the within-subjects factor, tested the effect of the VR intervention on eating and activity behaviors (pre to two-weeks) and cognitions (pre to post). Child age was included as a covariate in all analyses. Tests of normality were conducted on dependent variables across and within conditions using histograms, normality plots, skewness, and kurtosis metrics, and relevant dependent variables were transformed (e.g., cubed) when necessary. Assumptions of linearity and homogeneity of regression slopes were examined with scatterplots and interaction terms of condition and the relevant pre-test variable.

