All participants will provide demographic information at baseline and will have height and weight measured. To determine acceptability (Aim 2a), we will use the SUS and USE. Those randomly assigned to VR will also complete the PQ. To examine motivation to make behavior change (Aim 2b), participants will complete measures assessing self efficacy³⁹ and readiness to change behavior.⁴⁰ Specifically, they will complete the 16-item Self-Efficacy for Healthy Eating and Physical Activity measure⁴¹ and self-efficacy to lose weight will be assessed with the 8-item Weight Efficacy Lifestyle Questionnaire.^{42,43} Readiness to change behavior will be measured by the 6-item Readiness to Change Diet and Physical Activity Scale.⁴⁴ To examine behavioral beliefs and intentions (Aim 2c), participants will complete measures of behavioral cognitions from the Theory of Planned Behavior, including behavioral beliefs, attitudes, and intentions related to eating an activity behaviors.^{45,46} Finally, to examine behavior (Aim 2d), participants will complete self-report measures of activity and eating behavior over the past week, adapted from the Health Behavior in School-aged Children survey⁴⁷ at baseline and 2-week follow-up. The 10-item Positive and Negative Affect Schedule for Child and Parent⁴⁸ will be administered to control for mood and the child emotional eating scale serves as a measure of emotion regulation. Body esteem will be measured with several items from the Body Esteem Scale.^{49,50}

E. Study Design

E1. Overview or Design Summary

Study 2 will use a randomized pilot trial design to compare the VR experience to a video (created by team at WUSM) that provides child-friendly education on what types of foods are most nutritious and which are less healthy, and how the food they eat and activity they engage in now affects their health and future. The video will also encourage consideration of future consequences.

E2. Subject Selection and Withdrawal

E2.A. Inclusion Criteria

1. Parent is biological or legal guardian and can therefore consent on behalf of the child
2. Parent BMI is greater than or equal to 25 (overweight or obese)
2. Parent is under 80 years old and child is between 6 and 12 years old
3. Child BMI is at or above the 85th percentile for age and sex.⁵¹

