Participants will be recruited from the community using methods such as social media, flyers and word of mouth. Flyers will be posted in local (i.e., primarily St. Louis, MO) kid-friendly public spaces. Social media recruitment will occur over family-friendly social media and webpages. The social media advertisement will be posted on relevant WUSM accounts and to relevant web pages (i.e. family-based and health related pages and groups). We may also utilize participant recruitment services available through REC and REACH. Additionally, we may seek permission from WU PAARC to ask pediatric practices that are familiar with our lab through another study we are conducting (PLAN with families) if they would be willing to advertise for this study via postcards made available to give to patient families.

Interested individuals may call or email our research team whose contact information will be provided on flyers and social media posts and we may also reach out directly to some potential participants. If individuals are still interested after discussing the study directly with a research team member over phone and/or email, a research team member will conduct a brief phone screen to determine eligibility. If eligible, an appointment will be made for the parent and child to come into our lab at WUSM to review and sign consent and assent documents and then complete the study. Consent and assent information will be emailed to them so that they may have plenty of time to review these documents at their leisure. Upon arrival to our lab the informed consent process will take place, and subsequently the study. The informed consent process will occur in a private room in the Center for Healthy Weight and Wellness at Washington University School of Medicine in St. Louis. Participants will be consented according to the policies and procedures of the WUSM IRB, the IRB of Record for the study.

8/10/21

We will also use snowball sampling by reaching out to completed participants via email to ask if they would be willing to share recruitment materials with friends or family who may be interested in participating.

E2.E. Randomization Method

Using a random number generator, families will be randomly assigned to the experimental or control condition after baseline measures are taken. Those assigned to the experimental

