For individuals participating in the pilot study, there may be no direct benefits in terms of addressing overweight or obesity. However, individuals participating may benefit from knowing that their feedback is helping to design a digital tool that may ultimately address childhood obesity.

E2.G. Early Withdrawal of Subjects

Informed consent will make clear that participants may withdraw at any time with no penalty.

E2.H. When and How to Withdraw Participants

Taking part in this research study is voluntary. Participants may choose not to take part in this research study or may withdraw their consent at any time. They may withdraw by telling the research team they are no longer interested in participating in the study. If participants do not respond to phone calls or emails after 6 attempts to contact, they will be withdrawn from the study. Additionally, there will be 6 attempts to contact participants for the 2 week follow-up surveys via email or phone. There will be no penalty or loss of benefits to which they were otherwise entitled.

E2.I. Data Collection and Follow-up for Withdrawn Subjects

When a participant withdraws from the study, the research team will stop collecting data from them.

F. Study Procedures

F1. Screening for Eligibility

Eligibility will be assessed using the phone eligibility screen.

F2. Schedule of Measurements

Construct	Measure(s)	Participant(s) Taking	Time point
Eligibility			
Screen for disordered eating behaviors	Selected and Adapted Questions from ChEDE-Q	Parent self and proxy-report	Phone screen
Screen for overweight and conditions that could make it unsafe to participate in VR condition	Other Eligibility Questions In-lab height & weight	Parent self and proxy-report Parent & Child	Phone screen Pre
1. Acceptability (Aim 2a)			
Usability	System Usability Scale	Parent proxy-report	post
	Selected Child Interview Questions	Child self-report	
Ease of Use	Usefulness, Satisfaction and Ease of Use	Parent proxy-report	
	Selected Child Interview Questions	Child self-report	
Degree of immersion (for those in VR condition)	Presence Questionnaire	Parent self-report	
	Selected Child Interview Questions	Child self-report	
1. Motivation to Change behavior (Aim 2b)			
Self-Efficacy	Self-Efficacy for Healthy Eating and Physical Activity (SE-HEPA)	Child self-report,	Pre & post
Readiness to Change Behavior	Readiness to Change Diet and Physical Activity Scale	Parent self-report	Pre and post or 2-weeks depending on each question

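### The SAP describes change-score and two-time-point repeated-measures models but checks slopes on the pre-test value; a stated baseline-adjusted ANCOVA would clarify the model and usually tighten the estimates at almost no cost.

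*Combined protocol and SAP*

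**What the plan says.** Section J gives three kinds of model. For affect: "Univariate analyses of variance (ANOVA) models evaluated pre- to post-test changes in positive and negative affect by condition". For behaviours and cognitions: "Repeated-measures general linear models, with time as the within-subjects factor, tested the effect of the VR intervention on eating and activity behaviors", with pre and two-week values for behaviours and pre and post values for cognitions. Acceptability, measured only after exposure, is compared by t-test and is not at issue here.

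On covariates the section says only: "Child age was included as a covariate in all analyses". It does not name the model term that tests the intervention. It then reports that linearity and "homogeneity of regression slopes were examined with scatterplots and interaction terms of condition and the relevant pre-test variable".

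Three other places bear on the point:
- Section E2.E: "families will be randomly assigned to the experimental or control condition after baseline measures are taken".
- Section E2.D: "We plan to enroll 60 English-speaking children between the ages of 6 and 12", each with one guardian.
- Section D2, on the affect scale: it "will be administered to control for mood and the child emotional eating scale serves as a measure of emotion regulation". Section J lists no mood covariate.

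**The concern.** The slope check and the models do not fit together. Testing condition by pre-test interactions checks an assumption of a model that has the pre-test value as a covariate. Neither an ANOVA of changes nor a two-time-point repeated-measures model adjusted for age is such a model. The mood statement in section D2 is a further sign that the covariate account in section J may be incomplete, although it concerns a different variable.

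Two things are at stake, and bias is not one of them.

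- **Clarity.** The analysis cannot be reconstructed from the text. The unnamed test term matters too: if the condition main effect of the repeated-measures model were read as the treatment test, the pre-test score would dilute the effect by half.
- **Precision.** If the pre-test value was left out, a generally less efficient contrast was used. That contrast also over-corrects chance baseline differences. Section D1 sets out to evaluate efficacy and to inform later grants from 60 families, so interval width matters even in a pilot.

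**Working it through.** **Inputs from the documents.** 60 families (E2.D); baseline measured before randomisation (E2.E), so the pre-test value is a valid covariate; two time points per outcome and age as covariate (J). The documents state no power calculation, so there is no figure to reproduce.

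**Assumptions.** 30 families per arm; two-sided 0.05; pre-post correlation r of 0.3, 0.5 or 0.7; equal pre and post SDs unless stated. Effects are in SD units of the follow-up score. Age is in both models, and its own cost, common to both, is left out.

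**Formulas, per subject.**
- Change score: SD_pre² + SD_post² − 2r·SD_pre·SD_post.
- ANCOVA: SD_post²(1 − r²).
- Difference: (SD_pre − r·SD_post)², which is never negative and is zero only when r·SD_post = SD_pre.

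With equal SDs these become 2(1 − r) and 1 − r², so the ratio of ANCOVA to change score is (1 + r)/2. One extra covariate with N = 60 multiplies this by 56/55. Half-widths, detectable differences and power use central and noncentral t with 57 df (change) or 56 df (ANCOVA).

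| | r = 0.3 | r = 0.5 | r = 0.7 |
|---|---|---|---|
| Variance ratio (1 + r)/2 | 0.65 | 0.75 | 0.85 |
| × 56/55 | 0.662 | 0.764 | 0.865 |
| Net variance cut | 33.8% | 23.6% | 13.5% |
| 95% half-width, change (SD) | 0.61 | 0.52 | 0.40 |
| 95% half-width, ANCOVA (SD) | 0.50 | 0.45 | 0.37 |
| Detectable at 80% power, change (SD) | 0.87 | 0.74 | 0.57 |
| Detectable at 80% power, ANCOVA (SD) | 0.71 | 0.64 | 0.53 |
| Power at 0.5 SD, change | 36% | 48% | 69% |
| Power at 0.5 SD, ANCOVA | 51% | 59% | 75% |

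Example at r = 0.5: change, 2.00 × √(2 × 1/30) = 0.52; ANCOVA, 2.00 × √(2 × 0.75 × (56/55)/30) = 0.45.

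**Sensitivity.**
- Over r = 0.1 to 0.9 the net cut runs from 44% to 3%.
- With 25 per arm analysed and r = 0.5, the half-widths are 0.57 (change) and 0.50 SD (ANCOVA).
- If SD_post = 0.8·SD_pre, the large-sample cuts at the three r values are 50, 43 and 37%.
- If SD_post = 1.25·SD_pre, they are 22, 11 and 2%. The last is cancelled by the covariate cost: 0.981 × 56/55 = 0.999.

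**Chance imbalance.** Let D be the baseline difference between arms. With equal SDs the change-score estimate shifts by −(1 − r)D; the ANCOVA estimate does not shift. One standard error of D is √(2/30) = 0.26 SD, giving shifts of 0.18, 0.13 and 0.08 SD in the direction opposite to D.

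**Simulation check** (20,000 trials per r, no effect). Both methods averaged 0.00. The observed variance cuts were 34.6, 24.5 and 12.6%. The slopes of the estimate on D were −0.71, −0.51 and −0.29 for change, and within 0.01 of zero for ANCOVA.

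**Equivalence.** Regressing change on condition plus pre-test gives the same condition coefficient as regressing the follow-up score on condition plus pre-test. In one simulated data set both were −0.413.

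**Unnamed term.** If the condition main effect were taken as the test, power at 0.5 SD would be about 22% at r = 0.3, falling to 16% at r = 0.9.

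**The case against.** The strongest objection is that the gain may already have been realised. The slope check suggests that pre-test values were covariates in at least some models. The affect sentence could also describe a model of the post score adjusted for the pre score. That stands as a possibility, and it is why the request includes saying which models used the pre-test value. It does not explain the repeated-measures models, which as written give a change-score contrast.

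Second, r is unknown and may be high for measures taken just before and after a 10-minute exposure. At r = 0.8 the net cut is about 8%, and at 0.9 it is 3%. This stands: the larger figures may suit the two-week behaviours better than the immediate outcomes, though the documents settle neither.

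Third, section J allows transformed outcomes, so the SD-unit figures apply only on the scale analysed. This stands as a limit on the figures, and the revised text should state the scale.

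Fourth, section B2 frames the trial as a feasibility pilot giving initial impressions, and no power target was set. The power figures are therefore illustrations rather than a standard the trial failed. Narrower intervals would still serve the planning of a later trial.

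Fifth, section J is in the past tense, so a refit would be a later analysis and should be labelled as such. Emotional eating and body esteem are not named in section J, so modelling them extends the plan rather than repairing it.

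**Conclusion.** The point holds as a low-cost improvement in clarity and efficiency. It is not an error that biases the result. Section J does not let a reader tell whether pre-test values were adjusted for, and the models it describes do not match its slope check.

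If the pre-test value was left out, the net loss is material at r between 0.3 and 0.7: 34% down to 14% of the variance with equal SDs and 30 per arm. At r = 0.5, 60 families analysed by ANCOVA carry, in large samples, the information of 60/0.75 = 80 analysed by change scores. The loss is negligible near r = 0.9, and nil at r = 0.7 if the follow-up SD is 1.25 times the pre-test SD. All these sizes rest on assumed values of r, the SDs and the allocation. If the pre-test value was already in a change-score model, the estimate equals the ANCOVA one and only the wording is at fault.

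**What to change.** For each outcome with a pre-test and a follow-up value, fit the follow-up score on condition, the pre-test value of the same outcome, and child age. The outcomes are positive and negative affect, self-efficacy, the planned-behaviour cognitions, emotional eating, body esteem, eating and activity behaviours, and the readiness items that have a follow-up value (section F2 schedules these "Pre and post or 2-weeks depending on each question").

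Name the condition coefficient as the test and report it with a 95% confidence interval. Where an outcome is transformed, state the scale used for both the follow-up and the pre-test value. If pre-test values, or mood, were already covariates in some models, list which ones. The existing slope check then matches the stated model.

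The cost is one residual degree of freedom per model (57 to 56 with 60 families) and no new data, because the pre-test values are already scheduled. If the analyses are complete, the cost is a re-run, with the baseline-adjusted results labelled as added later and reported for all these outcomes.
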